8.2.1 Baseline Characteristics

The baseline data are presented on the basis of all screened subjects. They are collected at the Visit 1 and include: Medical & Dental History, Demographics, Inclusion & Exclusion Criteria, Concomitant Medications, Adverse Event Check, PPD, GM, CAL, FMPS, and Pain (see details in Section 5.1 and 5.3).

To assess balance in baseline characteristics, the distribution of each baseline variable of interest will be compared between the two treatment groups, i.e. test and control quadrants of the same arch. Continuous variables will be summarized using mean, median, standard deviation, 95% confidence interval, and range; testing between the two groups will be based on a two-sample t-test (or Wilcoxon rank-sum test as appropriate). Categorical variables will be summarized using counts and percentages, and differences between treatment groups will be assessed using a Chi-square test (or Fisher's exact test as appropriate).

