Registration Status	Straumann® Emdogain® used in the study is CE-marked and has received FDA-clearance (PMA approval No. P930021 S013). The investigational device will be used within its cleared indications.		

Primary Analysis	The primary analysis will be conducted after all subjects complete the 12 months post-surgery visit.
Primary Endpoint	
 • Clinical Attachment Level (CAL) change
Secondary Endpoints	
 • Change in Gingival Margin (GM) • Change in Probing Pocket Depth (PPD) • Change in Full Mouth Plaque Score (FMPS) • Change in Bleeding on Probing (BoP) • Change in root dentin hypersensitivity • Frequency of successful probing points (PPD < 5 mm) • Number of pockets that would normally be treated surgically that are converted to pockets that do not require surgical intervention.
Interim Analysis	Interim analysis will be done at 3 months post-surgery; optional interim analyses will be performed at 6 months and 9 months post-surgery.
Interim Analysis Endpoints	
 • Change in Clinical Attachment Level (CAL) • Change in Gingival Margin (GM) • Change in Probing Pocket Depth (PPD) • Change in Bleeding on Probing (BoP) • Change in root dentin hypersensitivity • Frequency of successful probing points (PPD < 5 mm) • Number of pockets that would normally be treated surgically that are converted to pockets that do not require surgical intervention. • Comparison of pain level between treatment groups at 1-2 days, 1 week, and 2 weeks after surgery.
Statistical Consideration	Statistics of the endpoints will be presented for raw values and change from baseline overall and by study center. The planned statistical testing to compare the treatment groups will be outlined in a Statistical Analysis Plan (SAP).
Safety	The patients will be monitored for adverse events by the Investigators until the end of follow-up for each patient. All device complaints and failures will be reported without delay to Straumann.
Countries in which the Study will be performed	United States and Canada
Number of participating centers	4 centers
Principal Investigators at Centers	[name], DDS [name] [name], DMD [name], DDS [name]. Dr. h.c. [name], M.Sc
Number of Subjects Planned to be Enrolled	50 subjects

Date of Study Initiation	September 2015
Date of Study Completion	Enrollment through December 2016; Follow-up complete for all subjects by December 2017
Sponsor	Institut Straumann AG

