3.3 Study Treatments

The workflow consists of:

Baseline evaluation:

The initial periodontal examination is conducted at the Visit 1 and includes a complete periodontal charting, including Pocket Probing Depth (PPD), Gingival Margin (GM), Bleeding on Probing (BoP), and Full Mouth Plaque Score (FMPS). This examination will be used to determine eligibility for the study based on inclusion/exclusion criteria (Section 3.7.1 and Section 3.7.2). Also, these are the baseline data used for the statistical analysis.

Treatment:

After qualification for the study, the subject will be randomized and treated with minimally invasive Scaling and Root Planing (SRP). An initial application of Emdogain® is performed during the SRP treatment for one quadrant (test). SRP alone will be performed in the contralateral quadrant (control). In addition, PrefGel® is applied on the test quadrant only (prior to the initial application of Emdogain®).

Based on the reported literature on how long Emdogain® remains in periodontal pockets^{11,10} a second application will be carried out 2-3 weeks after the initial Emdogain® application for the test quadrant to ensure longer presence of Emdogain® in the defect. Postoperative treatment is detailed in Section 5.2.3.

Re-evaluation and Follow-Up:

At 3 months, 6 months, 9 months, and 12 months after the initial application of Emdogain®, re-evaluations will be carried out in order to identify residual pockets that are indicated for perio-surgery (PPD ≥ 5 mm). This study design, including a dual application of Emdogain®, clearly aims to differentiate this treatment workflow from the approaches that have been reported in the literature.

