5.1.2 Inclusion and Exclusion Criteria

The inclusion and exclusion criteria will be evaluated at the screening visit. Subjects must fulfill all of the inclusion criteria and not meet any of the exclusion criteria. If this condition is not fulfilled, these patients will be considered as screen failures.

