5.2.1 Selection and Assignment of Quadrants

The inclusion and exclusion criteria will be reviewed (Section 3.7.1 and 3.7.2). If the subject remains eligible, randomized treatment assignment of a quadrant (test or control), will be done via randomization envelopes. At Visit 2, the Investigator or designee will open a sealed randomization envelope. The randomization envelope will identify the treatment assignment for the right and left quadrants, both in the same arch of the eligible patient. **Randomization envelopes must be open in sequential order.**

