8.2.2 Treatment Procedures

The treatment procedures data is presented on the basis of all enrolled patients. They are performed at Visit 2 and 3 (see details in Section 5.2).

Summaries of treatment procedures and supportive measures will be presented by assigned treatment group (test and control). Detailed information regarding the treatment procedures will be presented in listings (i.e. details per patient).

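### Section 8.2.1 bases the baseline data on all screened subjects, so pooled baseline summaries would include screen failures who were never randomised or treated

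*Combined protocol and SAP*

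**What the plan says.** Section 8.2.1 sets the population: "The baseline data are presented on the basis of all screened subjects". It places the data at the first visit: "They are collected at the Visit 1 and include: Medical & Dental History, Demographics, Inclusion & Exclusion Criteria". The list goes on to the probing measures, CAL and the full mouth plaque score. The next paragraph of 8.2.1 says that "the distribution of each baseline variable of interest will be compared between the two treatment groups, i.e. test and control quadrants of the same arch".

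Other sections use different populations or bear on who can be in them:

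- Section 8.2.2: "The treatment procedures data is presented on the basis of all enrolled patients". Sections 5.2.2 and 5.4.1 define enrolment as being randomised and having Emdogain applied at Visit 2.
- Section 5.1.2, on subjects who do not satisfy the criteria: "If this condition is not fulfilled, these patients will be considered as screen failures". Section 5.4.4 says that screen failures are replaced.
- Section 5.2.1: "If the subject remains eligible, randomized treatment assignment of a quadrant (test or control), will be done via randomization envelopes". This takes place at Visit 2.
- Section 3.3, on the Visit 1 examination that decides eligibility: "Also, these are the baseline data used for the statistical analysis".
- Synopsis, Statistical Consideration: "Statistics of the endpoints will be presented for raw values and change from baseline overall and by study center".

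**The concern.** Section 8.2.1 names a population and then prescribes a comparison that part of that population cannot enter. A screen failure has no test quadrant and no control quadrant.

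The practical risk is in summaries made per subject rather than per arm. A programmer who follows the first sentence of 8.2.1 would include screen failures in the tables of demographics and history. The same applies to the plaque score, which section 5.3.5 defines over the whole mouth and which therefore has no natural split by arm. Any probing summary pooled over quadrants would be affected too.

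A reader uses the baseline table to learn who was treated and how severe their disease was. That matters in a pilot which, by section 8.1, is meant to help define selection criteria. If the table contains people who were turned away, it does not answer that question, and its N does not agree with the tables that follow.

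**Working it through.** The plan gives no figure of its own on this point, so there is nothing to reproduce. The check is of the definitions, followed by arithmetic on what they imply for N.

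**Step 1. Is screened a loose word for enrolled?** No. Section 8.2.2 uses the enrolled population for treatment data. Section 8.2.4 lists consented subjects, screen failures and enrolled subjects as separate disposition groups. The protocol therefore distinguishes the terms.

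**Step 2. Would data on screen failures exist?** Probably in part. Sections 9 and 11.2.1 require case report forms for everyone who consents, and section 3.3 makes the Visit 1 charting the eligibility examination. The documents do not say whether charting is completed for a person who fails on history alone.

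**Step 3. Which tables can screen failures enter?**

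| Table | Can a screen failure appear? | Reason |
|---|---|---|
| Baseline by test and control quadrant | No | No quadrant assigned (5.2.1) |
| Change in CAL, surgery to 12 months | No | No surgery and no 12-month value (8.3.1) |
| Demographics, history, plaque score, pooled probing data at baseline | Yes, as 8.2.1 is worded | Population is all screened |

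Section 8.3.1 does not name the CAL analysis set. The second row follows from the definition of the endpoint.

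**Step 4. Effect on N.** Inputs from the documents: 50 enrolled (3.5) and dropout of up to 15% (8.1). Completers: 50 × (1 − 0.15) = 42.5, taken as 42. The screen-failure rate f is not given, so 10% to 40% is an assumption. It is also assumed that everyone randomised is treated. Screened N = 50/(1 − f), rounded up.

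| Assumed f | Screened N | Never randomised | Share of table | Share without 12-month CAL |
|---|---|---|---|---|
| 0% | 50 | 0 | 0% | 8/50 = 16% |
| 10% | 56 | 6 | 11% | 14/56 = 25% |
| 20% | 63 | 13 | 21% | 21/63 = 33% |
| 30% | 72 | 22 | 31% | 30/72 = 42% |
| 40% | 84 | 34 | 40% | 42/84 = 50% |

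**Step 5. Effect on a pooled mean.** The all-screened mean minus the enrolled mean equals s × D. Here s is the share never randomised and D is the mean in screen failures minus the mean in enrolled subjects. The documents give neither s nor D. If D were 1 mm in either direction, the shift would be 0.11 to 0.40 mm in that direction for f of 10% to 40%. If D were zero, there would be no shift.

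**Step 6. Effect on the treatment comparison.** CAL change is taken from each subject's own baseline, and both quadrants belong to the same subject. A screen failure supplies neither term, so the test-control difference is unchanged.

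**The case against.** The strongest reply is that the mixing cannot occur where it would matter most. Section 8.2 summarises the measurements by treatment group for non-missing subjects, and the quadrant comparison in 8.2.1 can only use people who have quadrants. This stands. It confines the problem to summaries not split by arm, but nothing in the text limits those to enrolled subjects. Section 8.2 also bases percentages on the N of a study population that it does not define.

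A reader might go further in three ways that the documents do not support:

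- *That the Emdogain effect is biased.* It is not, for the reason in Step 6.
- *That the baseline shift rivals the treatment effects sought*, for example the CAL differences of 0.5 to 0.7 mm in most rows of the table in the appended US instructions for use. A shift in a pooled baseline mean is a different quantity from a between-arm difference and cannot enter it. Its size and sign are also unknown. People excluded for smoking or recent antibiotics need not differ in pocket depth at all.
- *That screen failures are people with furcated, mobile or very deep-pocketed teeth.* Section 3.7.2 applies those rules to teeth. A subject fails on them only if too few qualifying pockets remain.

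Two further points have weight. Describing screened subjects may serve the pilot's aim of refining selection criteria; that argues for a separate table, not a mixed one. And section 8 defers detail to a separate statistical analysis plan, which could define the sets. No such definition is in the document supplied, and any separate plan should carry the same correction.

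**Conclusion.** The stated baseline population is wrong for its purpose and conflicts with the comparison in the same section. The consequence is modest. Baseline summaries not split by arm would misdescribe the treated population and would not share an N with the by-arm and change tables.

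The size of any shift in baseline values cannot be stated. The counts of 6 to 34 untreated people in a table of 56 to 84 depend on the assumed failure rates, and with no screen failures the discrepancy at baseline disappears. Screen failures are also not the only reason the tables would fail to reconcile. Dropout alone would leave about 8 of 50 enrolled subjects without a 12-month CAL value, so correcting the population does not by itself make baseline plus change equal the 12-month mean.

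**What to change.** Replace the first sentence of 8.2.1 with wording to this effect:

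> Baseline characteristics are summarised, and compared between quadrants, for all enrolled subjects (randomised and treated at Visit 2). Any subject randomised but not treated is listed separately. Screen failures are reported with reasons under 8.2.4; if their characteristics are summarised, this is done in a separate table.

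Naming the enrolled set keeps the wording in line with sections 5.2.2, 5.4.1 and 8.2.2. Section 8.2.4 already calls for reasons for screen failure.

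Also add a baseline row for subjects with a 12-month CAL value, so that baseline, change and 12-month values reconcile despite dropout.

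The cost is a short text change, one extra table row and, if wanted, a separate screen-failure summary. No new data or subjects are needed.

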2.1 Primary Objective

To evaluate the regenerative potential of Emdogain® by looking at differences in Clinical Attachment Level (CAL) between the test and control treatments.

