3.1 Type and Design of Study

This study is a post-market, prospective, split-mouth, controlled, multi-center study. Split-mouth design: each patient receives two treatments that are randomly assigned to either the right or left quadrant of the maxillary or mandibular arches.

- *Test Treatment:* Minimally Invasive Scaling and Root Planing (SRP) and applications of Emdogain®
- *Control Treatment:* Minimally Invasive Scaling and Root Planing (SRP) alone

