8.3.1 Primary Analysis of Primary Endpoint

Change in Clinical Attachment Level (CAL) between the surgery and 12 months post-surgery will be measured as the primary endpoint.

Statistics of the primary endpoint will present the seven-point scales (mean, standard deviation, minimum, 25% percentile, median, 75% percentile and maximum) of the change in CAL on the site of interest for each treatment group.

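### Section 8.2.1 compares quadrants of the same patient with independent-samples tests, and the protocol specifies no within-patient CAL difference or confidence interval

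*Combined protocol and SAP*

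**What the plan says.** Section 3.1 sets out the pairing: "each patient receives two treatments that are randomly assigned to either the right or left quadrant of the maxillary or mandibular arches". Section 2.1 states the primary objective as evaluating regenerative potential "by looking at differences in Clinical Attachment Level (CAL) between the test and control treatments".

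Section 8.2.1 then plans a balance check between the two treatment groups, which it defines as "i.e. test and control quadrants of the same arch". For continuous variables, "testing between the two groups will be based on a two-sample t-test (or Wilcoxon rank-sum test as appropriate"; for categorical variables it names a chi-square or Fisher's exact test. The same section opens by saying that "The baseline data are presented on the basis of all screened subjects", and its list of baseline data mixes patient-level items (history, demographics, the full mouth plaque score) with quadrant-level items (PPD, GM, CAL).

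For the primary endpoint, section 8.3.1 asks for mean, SD, minimum, quartiles and maximum "of the change in CAL on the site of interest for each treatment group". It gives no difference between treatments, no confidence interval and no test. The synopsis, the opening of section 8 and section 8.2 leave the comparative testing and the 95% intervals to a separate SAP. No SAP text is in the document.

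**The concern.** The design makes each patient his or her own control, and the only comparative method named in the protocol discards that. A two-sample t-test, rank-sum test, chi-square test or Fisher test treats the two quadrants as if they came from different people. Its variance omits the covariance between them.

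Two further features of section 8.2.1 do not fit a comparison between quadrants. Treatment is assigned to quadrants only at Visit 2 (section 5.2.1), so a screen failure has no test or control quadrant and cannot enter the comparison. A patient-level variable takes the same value on both sides, so it cannot differ between quadrants and a test of it carries no information.

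The primary analysis also stops short of the primary objective. Two per-arm summaries do not give the precision of the difference. Section 8.1 describes a pilot on which later studies will build. The SD of the within-patient difference is what those studies need for planning, and section 8.3.1 does not ask for it.

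**Working it through.** **Inputs from the document.** 50 subjects with up to 15% dropout (section 8.1): 50 × 0.85 = 42.5, so n = 42 completers is used. Section 8.1 gives no alpha, power, effect size, SD or correlation, so there is no power calculation to reproduce.

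**Assumptions.** Two-sided 5%; one value per quadrant per patient; equal SD in both quadrants (results are in units of that SD); within-patient correlation ρ of 0.3, 0.5 or 0.7, with 0 for reference.

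**Formulas.**

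- Standard error used by the two-sample test: SD × √(2/n).
- Correct standard error for pairs: SD × √(2(1 − ρ)/n).
- Ratio of the two: 1/√(1 − ρ).
- Real type I error of the two-sample test at nominal 5%: 2 × [1 − Φ(1.96/√(1 − ρ))].

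**Example at ρ = 0.5.** The ratio is 1/√0.5 = 1.41. The effective critical value is 1.96 × 1.41 = 2.77, which gives a two-sided error of 0.56%.

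| ρ | SE overstated by | Real type I error, formula | Simulated, n = 42 |
|---|---|---|---|
| 0 | 1.00 | 5.0% | 5.0% |
| 0.3 | 1.20 | 1.9% | 2.0% |
| 0.5 | 1.41 | 0.6% | 0.6% |
| 0.7 | 1.83 | 0.03% | 0.08% |

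The simulation used 50,000 trials per row. The paired t-test in the same trials stayed between 4.7% and 5.1%.

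**What can be recovered from section 8.3.1.** With complete pairs, the difference of the two arm means equals the mean within-patient difference. Its standard error does not follow from the arm SDs, because the variance of the difference is SD₁² + SD₂² − 2ρ·SD₁·SD₂ and the planned summaries do not report ρ.

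**If the section 8.2.1 approach were carried over to CAL (conditional).** At n = 42 the unpaired 95% CI half-width is 1.96 × √(2/42) = 0.43 SD at every ρ. The paired half-width is 0.43 × √(1 − ρ). Simulated power is for a true difference of 0.5 SD.

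| ρ | Half-width, unpaired | Half-width, paired | Power, two-sample | Power, paired |
|---|---|---|---|---|
| 0.3 | 0.43 SD | 0.36 SD | 64% | 76% |
| 0.5 | 0.43 SD | 0.30 SD | 67% | 89% |
| 0.7 | 0.43 SD | 0.23 SD | 71% | 98% |

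**The case against.** The strongest reply is that the tests in section 8.2.1 serve baseline balance only. Nothing in the protocol assigns them to CAL or to any other outcome, and endpoint tests and intervals are expressly left to the SAP. This is also a pilot that makes no power claim and plans descriptive statistics. All of that is correct, and it limits the point. A reader might infer that the pairing will be ignored throughout and the CAL difference never estimated. The document does not support that, because the SAP may specify a paired analysis. What can be said is that the protocol specifies none.

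A reader might also infer that the primary summaries are themselves wrong. They are not. Per-arm means, SDs and quartiles are valid marginal descriptions, and section 8.3.1 puts no interval on a difference that could be in error. Withdrawal is by subject (section 5.4.2), so both quadrants would normally be lost together and the mean difference could still be read from the arm means. The analysis is incomplete, not invalid.

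Finally, section 8.2.1 compares selected baseline variables and does not say that age or sex will be tested. That reading is an inference. The section does, however, fail to separate patient-level from quadrant-level variables.

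The deferral leaves the baseline tests untouched, because they are already fixed in the protocol. The SAP is meant to supplement section 8, where the only comparative method named is unpaired.

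**Conclusion.** The point holds in two parts. First, section 8.2.1 is wrong as written: it fixes independent-samples tests for paired quadrants and bases baseline data on a population that includes people with no quadrant assignment. For ρ between 0.3 and 0.7 the standard error is overstated 1.20 to 1.83 times and the real type I error falls to between about 1.9% and under 0.1%, so the balance check would tend to miss a real imbalance. Second, the protocol does not specify a within-patient CAL difference or its interval, although that difference is its primary objective.

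The error is conservative. A reader might infer a risk of false-positive findings, but with positive correlation and one value per quadrant the effect is the reverse: intervals too wide and power lost. For CAL this is conditional on the section 8.2.1 approach being carried over, which no text plans. The values of ρ and the 0.5 SD effect are assumptions, since the document gives neither. Section 8.2.1 does not say how sites are reduced to one value per quadrant, and the stated direction does not cover an analysis that enters individual sites as independent observations.

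**What to change.** **Section 8.2.1.** Compare quadrant-level baseline values (PPD, GM, CAL, and BoP as the percentage of bleeding sites per quadrant) as within-patient differences with a paired 95% CI, using a paired t or signed-rank method. Present patient-level variables once, untested, for enrolled subjects. Account for screen failures in the disposition summary, where section 8.2.4 already places them.

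**Section 8.3.1.** Derive one CAL change per quadrant over the sites on study teeth that measured 5–8 mm at baseline. Report as the primary result the mean within-patient test minus control difference with its 95% CI, from a paired analysis or from a model with patient as random effect and quadrant baseline CAL as covariate. Report the SD of the within-patient difference for use in planning later trials. Keep the per-arm summaries as support, and make the SAP say the same.

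**Cost.** Protocol and SAP wording and a few lines of code. No new data or visits.
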